9.4.2 ANALYSIS OF THE PRIMARY ENDPOINT(S)

The main goal of the study is to understand the neurophysiological basis of human cognition. This will require integrated analysis of clinical, neurophysiological, anatomical, video and behavioral datasets.

Analysis of Electrophysiological Data: Some of the analysis will be performed at Mount Sinai, and some will be performed at collaborating sites. Any data sent to other sites will be de-identified. Typically, iEEG recordings are amplified x10000, analog filtered (0.01-1000 Hz) with $> 1\text{kHz}$ digitization rate, re-referenced to a common average or bipolar reference scheme offline and high-pass filtered at 0.1-1 Hz with a symmetrical (phase true) finite impulse response (FIR) filter (35 dB/octave roll-off). Channels with a low signal-to-noise ratio (SNR) are identified and deleted

(i.e., 60 Hz line interference, electromagnetic equipment noise, amplifier saturation, poor contact with cortical surface). Additionally, channels are visually inspected by a neurologist or research team member to exclude epochs of aberrant or noisy activity (typically < 1% of data points). A photodiode recorded screen updates in the behavioral task, recorded in the electrophysiological system as an analog input and used to synchronize behavioral and electrophysiological data. In some cases, different synchronization (through an audio feed into an analog channel or through TTL pulses) may be carried out. Data analysis is carried out in MATLAB and R using custom scripts and electrophysiological analysis toolboxes (e.g. Fieldtrip). Data for each channel is down sampled to 1KHz and filtered into high-frequency activity (HFA; 70–200 Hz) using a two-way, zero phase-lag, finite impulse response band pass filter to prevent phase distortion. Alternatively, time-frequency representations are created using wavelets, or equivalent methods, using linearly or logarithmically spaced frequencies, which allows for comparisons between time-varying high-frequency and low-frequency signals on an equal footing. This is especially important for iEEG signals, which are generally nonstationary and have time-varying phase components. We will also measure coherence and phase synchronization to quantify the degree to which oscillatory effects are synchronized across brain regions.

When analyzing physiological data recorded at many electrode sites for effects at many frequencies, it is necessary to correct for multiple comparisons. Using standard statistical methods, such as a t-test or a Wilcoxon rank-sum test, and setting an arbitrary p-value threshold for the significance of the difference between two conditions does not account for the possibly high number of false positives by chance. Therefore, to generate an unbiased empirical estimate of the Type I error rate, we will use a bootstrap procedure, a method often used to handle correlations among statistical comparisons of electrophysiological measures. The bootstrap procedure first entails generating a large number (>1000) of random samples of the experimental data by randomly swapping items from each of the categories being compared. The same randomization is used across electrodes to control for between-electrode correlations. By running the statistical tests on each of the shuffled datasets one generates a distribution of statistics from which one can then determine the statistical threshold that would achieve a given Type I error rate.

Analysis of video data: A video recording of the patients will be obtained, either through the standard video-EEG procedure included as part of the standard of clinical care or through a dedicated research video camera in the same room. The video data may be analyzed to identify patient behavioral or mood states (e.g. sleep, awake, communication, laughing, etc.). These analyses will be carried out either by research personnel or using dedicated software. The resulting datasets will be kept in a secure location together with the electrophysiological and other data from the patient.

Electrode Localization: For the proposed research, electrode locations are determined using co-registered postoperative CTs and preoperative MRIs by an indirect stereotaxic technique (Talairach & Tournoux, 1988). After normalization, locations can be reported by means of stereotaxic (Talairach) coordinates. This format uses three numbers (X, Y, Z) to describe the distance from the Anterior Commissure (the “origin” of Talairach space). The X, Y, Z dimensions refer to left-right, posterior-anterior, and ventral-dorsal, respectively (i.e., 38 X 64 X 58 mm refers to a point in the right-posterior-dorsal region of the brain). Region-of-interest analyses can be conducted and better compared across participants by normalizing the brain using Talairach coordinates. The Talairach atlas serves as a reference so that one may know what region of the “idealized” brain is being described. These techniques are commonly used at Mount Sinai now and may aid in clinical patient care by providing accurate anatomical localization for individual electrodes.

9.4.3 ANALYSIS OF THE SECONDARY ENDPOINT(S)

The secondary endpoints will involve analysis of behavioral modulation resulting from electrical modulation of neuronal activity. As such, they will be task specific, but in most instances this will entail estimation of a behavioral (for example, proportion of remembered items in a memory task) or computational (derived from behavior through the application of computational models) metric of interest in pre-stimulation (baseline) and stimulation conditions. We will carry out within-patient comparisons to account for inter-patient variability, and in most instances will carry out two-tailed statistical tests (e.g. two-tailed t-test) to compare individual behavioral/computational estimates.

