1 PROTOCOL SUMMARY

1.1 SYNOPSIS

Title:**Study Description:**

Electrophysiologic studies of cognition in epilepsy patients

In this study, we seek to study how brain activity contributes to the generation of actions, emotions, memories, and other thought processes. To do that, we propose to examine brain activity recorded in patients undergoing neurosurgical interventions for treating epilepsy. Specifically, we leverage the fact that intractable epilepsy patients are surgically implanted with electrodes that allow recording the brain's electrical activity. Each electrode provides a readout of electrical activity in a different brain area, and therefore a way to measure brain activity in a very precise way, both anatomically and temporally, something that is very difficult to achieve otherwise in human subjects. We combine these recordings of electrical activity with tasks designed to test different aspects of behavior and thought, such as memory, decision-making, spatial navigation, etc. These take the form of short computer games that the patients will play while their brain activity is recorded using the clinically implanted electrodes. We will subsequently analyze the brain data, together with the patients' behavior and information about the location of each electrode, to derive information on how brain activity in different brain areas is related to behavior. In some cases, we will use special electrodes that allow very precise examination of neural activity (i.e. examine activation of single neurons, compared to large populations of neurons using other approaches) or use small amounts of electrical currents to stimulate specific brain areas to test their contribution to behavior. This will provide us with a more detailed understanding of the neurobiology of thought and provide causal observations of the contributions of individual brain areas. In a subset of patients that are clinically determined to undergo treatment resection, we will collect tissue samples for molecular analyses. This combination of electrophysiological recordings and behavioral tasks provide a unique opportunity to understand the contribution of brain processes to normal thoughts and behavior, as well as how these are affected in disease states (i.e. epilepsy, depression).

Objectives* :

Primary Objective:

Study the neurophysiological basis of human cognition and actions.

Endpoints*:

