3 OBJECTIVES AND ENDPOINTS			
OBJECTIVES	ENDPOINTS	JUSTIFICATION FOR ENDPOINTS	PUTATIVE MECHANISMS OF ACTION
Primary			
Investigate the neurophysiological correlates of human cognitive processes. The approach involves the analysis of the brain's electrical activity during computer-controlled cognitive/perceptual tasks, to determine how behaviors that occur during these tasks correlate with changes in electrical activity measured inside the human brain and on the scalp.	The primary endpoint for each task tested will be the number of estimated subjects required for appropriate powerful statistical testing –an estimated 10-20 subjects depending on the	Achieving appropriate statistical power for each task.	Measuring neuronal activity in neuronal populations.

OBJECTIVES	ENDPOINTS	JUSTIFICATION FOR ENDPOINTS	PUTATIVE MECHANISMS OF ACTION
	anatomical coverage of individual patients.		
Secondary			
Investigate the causal involvement of individual brain areas in cognitive processes through targeted electrical stimulation.	The primary endpoint for each task tested will be the number of estimated subjects required for appropriate powerful statistical testing—an estimated 10-20 subjects depending on the anatomical coverage of individual patients.	Achieving appropriate statistical power for each task.	Modulation of neuronal activity and behavior through neural stimulation.
Tertiary			
Characterize the genetic and molecular composition of human brain tissue to reveal differences in genetic expression and its relationship to electrophysiological and clinical measures.	The primary endpoint will be the number of estimated subjects required for appropriately powerful statistical testing for each clinical diagnosis, comorbidity or electrophysiological metric under study—an estimated 20 subjects per set.	Achieving appropriate statistical power for transcriptomics studies.	Gene transcription patterns in resected tissue.

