Brain Stimulation: Electrical brain stimulation is a routine procedure in the EMU for localization of brain function and is frequently performed in patients with intracranial electrodes. We plan to use similar focal currents, using macroelectrodes to stimulate the brain, during cognitive tasks to help localize and define cognitive networks. The patient's baseline performance on specific tasks will be established on trials without stimulation and compared to trials with stimulation in specific regions and statistically analyzed. For stimulation, we may employ the stimulation hardware routinely used for clinical mapping (e.g. Nicolet cortical stimulator) or an equivalent research device (e.g. ATLAS Stim Headbox - High Density, part number: 31-0601-0132) using identical stimulation parameters as specified below. The electrical current will be kept at or below the same safe levels as used in standard clinical cortical mapping. Safety limits have been established for decades (McCreery, et al. 1990; Gordon et al., 1990, Shannon 1992). Here, we will apply stimulation while subjects perform cognitive tasks at levels far below the safety limits identified by histological analysis for stimulation protocols (McCreery, et al. 1990; Gordon et al., 1990). Stimulation studies will be performed using currents not exceeding 10mA, below the accepted safety limits for charge density (Shannon 1992), and in line with previous studies. There is no evidence that stimulation of the type to be performed in this study causes any patient risk. The only significant change to the patient's routine in the proposed studies is that brain stimulation will be performed for longer periods and sometimes in different locations than required for standard evaluation. Patients will be asked frequently if they would like to continue or stop testing, and testing will be halted at any signs of patient discomfort or fatigue. Electrical stimulation also provides the opportunity to measure changes in neurotransmitter concentration via voltammetry techniques that have been recently developed for safe use in human subjects (Kishida 2018).

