9 STATISTICAL CONSIDERATIONS

9.1 STATISTICAL HYPOTHESES

Primary endpoints: Investigate the neurophysiological correlates of human cognitive processes. We hypothesize that modulations in neural activity, as recorded by electrophysiological or electrochemical techniques, will be associated with different cognitive aspects of the behavioral tasks that the patients will complete. Specifically, we expect that cognitive brain functions will localize to a variety of brain areas, including temporal and prefrontal regions, with electrophysiologic signatures in the theta (4-8Hz) and high-gamma (70-200 Hz) frequency ranges. Scientists have theorized that cyclic changes in the brain's electrical activity (brain oscillations) play a fundamental role in memory function. Studies have focused on the theta (slow) rhythm which oscillates in the 4-8Hz frequency range and high gamma activity which appears in the 70 to 200 Hz frequency range because these neural signatures appear prominently during a wide range of cognitive tasks and are hypothesized to be the cause of all neural activity - our thoughts, feelings and perceptions. The relationship between brain oscillations and neuronal activity is largely unexplained so our study aims to investigate the correlation between brain oscillations and the neuronal activity of

human cognition. We will also investigate the contribution and information processing capabilities of individual neurons.

Secondary endpoints: investigate the causal involvement of individual brain areas in cognitive processes through targeted electrical stimulation. We hypothesize that modulation of brain electrical activity through targeted stimulation will reversibly affect patient behavior. Specifically, we expect that stimulation of prefrontal cortical areas (i.e. orbitofrontal cortex) will result in changes in associated behavior (for example, in choices during decision-making behavior) that will be sampled through behavioral tasks.

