In the case of behavioral analyses (i.e. for secondary endpoints), behavioral metrics or latent model parameters will be estimated from the behavioral data. To compensate for potential variability across patient behavioral strategies and behavior, we will whenever possible employ a within-subject analysis by completing a baseline behavioral task pre-stimulation (either before or during hospital admission). If possible, we will also test for lingering behavioral effects by carrying out behavioral testing post-stimulation.

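### The stimulation analysis compares only stimulation with no stimulation, so it cannot by itself support the area-specific causal conclusion named in the secondary objective

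*Combined protocol and SAP*

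**What the plan says.** The secondary objective in section 3 is to "Investigate the causal involvement of individual brain areas in cognitive processes through targeted electrical stimulation". The synopsis (section 1.1) says that the stimulation work will "provide causal observations of the contributions of individual brain areas". The hypothesis in section 9.1 names a region: "stimulation of prefrontal cortical areas (i.e. orbitofrontal cortex) will result in changes in associated behavior".

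The comparators are described in three places:

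- Section 9.4.3 estimates a behavioural or computational "metric of interest in pre-stimulation (baseline) and stimulation conditions" and compares them within patient, in most instances with a two-tailed test such as a t-test.
- Section 4.1 (Brain Stimulation) says that baseline performance will be "established on trials without stimulation and compared to trials with stimulation in specific regions and statistically analyzed".
- Section 9.4.1 plans, whenever possible, a baseline task before stimulation, taken before or during the admission. If possible, there is also a post-stimulation test for lingering effects.

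No section describes a sham condition, a control site, a contrast between regions or a site-by-stimulation term. Section 6.3 (randomization and blinding) and section 6.1.1 (description of the manipulation) both read N/A.

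Section 9.2 bases the stimulation experiments on a 10-point difference in risk-preference score, power above 85% and a two-sided 0.05 test. The expected sample is 10–20 patients. No SD is given.

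**The concern.** The objective and hypothesis are about where stimulation acts. The planned test is about whether it acts. An on/off difference is the sum of two parts: the effect of perturbing the target area, and whatever happens to a patient stimulated at any contact (feeling something, being distracted, being more alert). The test responds to the sum.

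This is separate from when the baseline is taken. Interleaving stimulated and unstimulated trials would reduce practice and fatigue effects, but the two parts would still be combined.

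At stake is the wording of the conclusion. A positive result supports the statement that stimulation at this site changed behaviour. Followed as written, the plan would let the same result be read as evidence for that area in particular.

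**Working it through.** **1. Target and comparator side by side.** Sections 1.1, 3 and 9.1 refer to individual areas, with orbitofrontal cortex as the example. The comparators in 4.1, 9.4.1 and 9.4.3 are unstimulated trials, a pre-stimulation baseline and an optional post-stimulation test. None is stimulation at another place.

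Write the expected on/off difference as Δ = A + N, where A is the area-specific part and N the part common to stimulation anywhere. The planned test is of Δ = 0. When A = 0 and N ≠ 0, it rejects at its power for N.

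**2. The plan's own power figure.** Inputs from section 9.2: δ = 10 points, n = 10–20 patients, two-sided α = 0.05, power above 85%. Without an SD the figure can be neither reproduced nor refuted. I therefore solved for the SD of the within-patient difference that gives exactly 85% in a paired t-test:

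power = P(|T| > t₀.₉₇₅,ₙ₋₁), with T noncentral t on n − 1 df and noncentrality δ√n / SD.

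| n | SD for 85% | noncentrality at 10 points |
|---|---|---|
| 10 | 9.4 | 3.37 |
| 15 | 12.0 | 3.22 |
| 20 | 14.2 | 3.16 |

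**3. Rejection rate with no area-specific effect (A = 0).** Same formula and SDs, with N in place of δ. The values of N are assumptions; the documents give none. For example, at n = 10 and N = 5 the noncentrality is 5 × √10 / 9.38 = 1.69.

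| Nonspecific shift N | n = 10 | n = 15 | n = 20 |
|---|---|---|---|
| 3 points | 14.8% | 14.7% | 14.7% |
| 5 points | 32.6% | 32.4% | 32.3% |
| 10 points | 85% | 85% | 85% |

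The last row shows that a purely nonspecific 10-point effect is declared significant exactly as often as a purely area-specific one.

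**4. What a site contrast would do.** The contrast is (change at target) − (change at comparison site), with expectation (A_target − A_comparison) + (N_target − N_comparison). If the nonspecific parts are equal and neither site is involved, the expectation is 0 and the rejection rate is 5%. A simulation of 20,000 runs at n = 10 and n = 20 gave 5.0–5.2%. If the nonspecific parts differ, the rate exceeds 5%. A 5-point difference gives about 19% with the larger SD of step 5, or 32–33% with the SD unchanged.

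**5. What the contrast costs.** If the two site effects have equal variance and correlation ρ, the SD of the contrast is SD × √(2(1 − ρ)).

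- ρ = 0: the factor is 1.414. At n = 10 the SD is 9.38 × 1.414 = 13.3, and power for a 10-point site difference falls from 85% to 56.6% (56.4% at n = 20). Regaining 85% would take 18 patients instead of 10, or 38 instead of 20.
- ρ = 0.5: the factor is 1 and power stays at 85%.
- Comparison site truly involved at 5 points, target at 10, ρ = 0: the expected contrast is 5 points and power is about 19%.

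These figures apply to a within-patient contrast only. A comparison across patients is not covered.

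**The case against.** The strongest reply is that the objective asks whether an area is involved, not whether it is involved more than others. Section 9.1 itself expects cognitive functions to localize to a variety of areas, including temporal and prefrontal regions. Another stimulated contact may therefore be truly involved, and a null contrast against it would not show that the target is uninvolved. The 19% in step 5 shows the cost. This stands. It rules out making every area claim depend on a contrast with whatever other contact is available, and it means comparison regions must be named in advance.

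Section 9.4.3 also calls these analyses task specific and is hedged with phrases such as in most instances, so a task could add a control site. That is true, and a reader should not infer that the plan forbids one. But nothing requires or describes one.

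A reader might infer from section 4.1 that off-target sites will often be in the data and go unused. The text does not support this. Its remark about different locations means locations other than those needed for the standard evaluation. It does not say that several sites are stimulated in one patient during one task, and no number of sites per patient or task is given anywhere.

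Nor does a site contrast guarantee a 5% error rate; that needs equal nonspecific effects at both sites. Current spread is not a good example of a nonspecific effect either. It is local, and a distant comparison site would not remove spread from the target to its neighbours.

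**Conclusion.** The concern holds in this form: with no-stimulation comparators only, section 9.4.3 can establish that stimulation at a site changes behaviour, but not that the effect is specific to that area. This follows from the objective and the comparators alone and does not depend on any SD.

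The rates of about 15% and 32–33% rest on three assumptions: a paired t-test on 10–20 patients, an SD set to give exactly 85% power, and nonspecific shifts of 3 and 5 points that have no source in the documents. They show how the test behaves if such shifts exist, and are not evidence that they do.

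The remedy is mainly a limit on what is concluded, with a contrast added where the data allow it. It should be done, and it does not invalidate the on/off test.

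**What to change.** In section 9.4.3:

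1. Keep stimulation versus no stimulation as the test that stimulation changes behaviour.
2. State that a positive result will by default be reported as an effect of stimulation at that site, and not as evidence specific to that area.
3. Where the same task has been run with stimulation in more than one region, also estimate the site-by-stimulation contrast: change in the hypothesised region minus change in comparison regions named beforehand as not expected to support the task. Do this within patient where possible, otherwise across patients in a mixed model with patient as random effect. Report the estimate with its confidence interval.
4. Make area-specific statements only when that contrast supports them.

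This asks for no additional stimulation. The cost is SAP wording, a list of comparison regions per task and one further model term where it can be estimated. Because the number of sites per patient or task is not stated, the contrast may often be unavailable, and those tasks lose the area-specific claim. Where it is available within patient, power is about 56% instead of 85% if the site effects are uncorrelated with equal variance. It is higher with positive correlation, and lower if the comparison region is itself involved.
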